5.0 Inclusion and Exclusion Criteria/ Study Population

Patients will be referred from other psychiatrists or may self-refer after hearing about the trial from email broadcasts, or mailings to psychiatrists. At least during the first year we will not formally advertise.

Rationale for Subject Selection Procedures. A summary of inclusion/exclusion criteria for Phase 1 study entry are presented in Table E.1.

A brief note about this clinical trial and R-DOC criteria. While we embrace the notion of RDOC, and have listed a continuum of behavior (emotion regulation) and a well-defined target (ACC inhibition), we need to compare whether this new form of TMS improves on the current state of the art. All prior TMS studies in depression have used DSM-IV criteria for inclusion and exclusion. Thus, in order to reasonably compare this trial to those done in the past, we will resort to DSM-IV criteria for inclusion and exclusion criteria, while still examining the continuum of behavior and assess target engagement.

Table E.1 Inclusion and Exclusion Criteria for Study Entry

1. Diagnosis of unipolar major depressive disorder, in a current major depressive episode, without	SCID-P to derive DSM-IV criteria
psychotic features	
2. Pretreatment Hamilton score ≥ 20	Hamilton Rating Scale for Depression [24-item]
3. Age between 21 and 70 years	Self-report
4. Fixed and stable antidepressant medications for 3 weeks prior and during the rTMS trial. Limit on benzodiazepines to lorazepam (or equivalent) up to 3 mg every day	Physician evaluation
5. Moderate level of resistance to antidepressant treatment in the current episode, defined as failure of 1-4 adequate medication trials or intolerance to at least 3 trials, and duration of current episode ≤ 3 years	Antidepressant Treatment History Form (ATHF) and physician evaluation
6. No primary diagnosis of schizophrenia, schizoaffective disorder, other [non mood disorder] psychosis, depression secondary to a medical condition, mental retardation, substance dependence or abuse within the past year (except nicotine), bipolar disorder, psychotic features in this or previous episodes, amnestic disorder, dementia or MMSE ≤24, delirium, obsessive compulsive disorder, post-traumatic stress disorder, panic disorder	Physician evaluation, Mini Mental Status Exam (MMSE)
7. No current Vagus Nerve Stimulation	Medical history

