8. No history of failing to respond to an adequate course of ECT in this or any episode, and no ECT within the past 3 months	ATHF and physician evaluation
9. No contraindication to MRI	Physician evaluation; medical history
10. No contraindication to rTMS (history of neurological disorder or seizure (except induced by ECT), increased intracranial pressure, brain surgery, or head trauma with loss of consciousness for >15 minutes, implanted electronic device, metal in the head, or pregnancy)	Physician evaluation; medical history; MRI; urine pregnancy test
11. No unstable autoimmune, endocrine, viral, or vascular disorder. No unstable cardiac disease, uncontrolled hypertension, or sleep apnea	Physician evaluation; medical history
12. No active suicidal intent or plan, or history of attempt within the past 12 months	Physician evaluation
13. Willing to provide informed consent	

Patients with unipolar major depression meeting the above criteria will be enrolled. The baseline HRSD score (24-item) must be >20. To ensure that baseline levels of depression severity are stable at the time of study enrollment, patients will be dropped if they show > 30% improvement in the HRSD score from the time of initial intake (e.g., screening) to the baseline assessment.

All subjects will have an MRI scan after obtaining consent but before being randomized.

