Because prior work has suggested that response to rTMS is suboptimal in depressed patients with psychotic subtype, patients with any history of psychotic features will be excluded. Another suggested predictor of response with rTMS is age. While prior work has suggested that the efficacy of rTMS may be lower in the elderly^{16, 17}, this is now thought to relate to the presence of cortical atrophy, resulting in an under-dosage of rTMS. We will include patients up to the age of 70, which will permit us to assess the utility of this dosage adjustment method.

Unlike some prior work with rTMS, this study will test the efficacy of rTMS with patients on fixed but stable concurrent psychotropic medications. This will eliminate the need for all patients to undergo medication washout prior to rTMS, and will greatly facilitate recruitment. Patients who have taken benzodiazepines chronically may not be able to tolerate dosage reduction to no more than 3 mg of lorazepam, and additionally may be at risk for withdrawal associated lowering of seizure threshold. Such patients will therefore be excluded. Another aspect of the patient's current depression treatment program may include psychotherapy. With the intention to study the stand-alone efficacy of SYNC or NON-SYNC rTMS in the absence of other treatment regimens, we will limit the frequency of visits with

the referring psychiatrist and/or therapy to no more than once per month. Additionally, no new psychotherapeutic relationships will be initiated during the study.

Patients with comorbid neurological disorders will be excluded as these may affect response rate, and may represent a contraindication to rTMS. Conditions increasing risk of seizure (e.g., history of seizure, head trauma, increased intracranial pressure, or space occupying brain lesion) will be excluded because seizure is a known risk of rTMS. Pregnant women will be excluded because of the unknown risks of the magnetic stimulation on the fetus. In the future, if rTMS becomes a proven treatment for major depression, its safety in the context of pregnancy should be studied¹⁸.

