Research Procedures. We have described above the potential risks of the research procedures. If the patient shows deterioration in their clinical status, we will stop him/her from proceeding in the study, and coordinate appropriate follow-up care with the referring psychiatrist. Certified TMS operators will visually determine the motor threshold using parameter estimation by sequential testing (PEST). We will minimize the risk of seizure by prescreening patients with an MRI scan of the head, and will tailor each person's stimulation parameters to their own motor (and indirectly seizure) threshold. We will exclude patients on all psychotropic medications (except for lorazepam at no greater than 3 mg/d) and all stimulants (except for caffeine). These could potentially lower the seizure threshold. We will minimize hearing damage by having all patients wear earplugs to protect their hearing during the TMS and MRI sessions. We will minimize the anxiety due to the MRI procedure by offering patients a mirror to look outside the bore at a screen and provide continuous feedback and update of procedure to patients in the scanner. All magnetically sensitive objects such as credit cards and electronic devices such as hearing aids, watches, and calculators will be put in a container to prevent damage from the magnet. The patient will be stimulated in clinical settings designed for TMS. An Ambu bag will be available. Patients will place earplugs in their ears.

Participation in the study will be treated as confidential, as will all records. The Food and Drug Administration and Institutional Review Board will have access to the records, but patients will be assigned study numbers for record keeping purposes. We will protect the identity of our patients by keeping the data in file cabinets in the PI's locked office, to which only they have a key.

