15.0 Risks to Subjects

Potential risks related to TMS: Based on previous clinical work of left prefrontal rTMS in depression, and in various other psychiatric disorders as well as others researchers published and communicated experiences, we hypothesize that NON-SYNC left prefrontal rTMS (as intended in this grant) is an effective antidepressant treatment, and that SYNC rTMS will be at least as effective or better. This study is an important necessary step to characterize the safety, and efficacy of the antidepressant effect. **Potential worsening of depression symptoms with TMS**: Several studies have so far demonstrated the feasibility of rTMS in depression without any alarming indicators of exacerbation of symptoms. We

will work closely with the patient to familiarize them with the experimental setup. The BSL team members at MUSC are experienced with the procedure and are among the leading experts in the field of brain stimulation and TMS. We will also monitor closely for worsening suicidal ideation or increasing hypomania or mania.

Potential risk of a seizure: Unlike ECT, in routine use, TMS stimulates the neurons at a sub-convulsive level, although less than 50 seizures have been noted in the literature. Six of them have been in healthy volunteers (without any history of seizures, brain masses or traumatic brain injuries). The risk of seizure induction is related to the intensity, duration, frequency and rest interval of stimulation. Following the adoption and widespread use of the safety guidelines from an NINDS workshop on TMS, 10 seizures have been reported since 1997 and they involved parameters of "higher settings" then the "safe range" ¹⁹⁻²¹, or interactions of TMS with medications known to lower the seizure threshold. To our knowledge, stimulation with the parameters and settings we propose to use does not cause seizures, even the SYNC settings. We will carefully titrate each person's stimulus intensity to his or her motor threshold, before beginning treatment. Our study patients will be off neuroleptics and other psychotropic medications for at least 2 weeks (except benzodiazepines).

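### Section 5.0 enrols patients on stable antidepressants, while Section 13.0 excludes patients on all psychotropics except lorazepam as a seizure safeguard; both rules cannot hold.

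*Combined protocol and SAP*

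**What the plan says.** Section 5.0, Table E.1 item 4, sets the entry rule for depressed patients: "Fixed and stable antidepressant medications for 3 weeks prior and during the rTMS trial". The same item caps benzodiazepines at 3 mg of lorazepam, or an equivalent, per day. The text after the table says "Patients with unipolar major depression meeting the above criteria will be enrolled". The later rationale in Section 5.0 shows that item 4 is deliberate: "this study will test the efficacy of rTMS with patients on fixed but stable concurrent psychotropic medications". It adds: "This will eliminate the need for all patients to undergo medication washout prior to rTMS, and will greatly facilitate recruitment".

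Section 13.0, under Research Procedures, lists measures to reduce seizure risk. Among them: "We will exclude patients on all psychotropic medications (except for lorazepam at no greater than 3 mg/d) and all stimulants (except for caffeine". The reason follows at once: "These could potentially lower the seizure threshold".

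Section 15.0, in the paragraph on seizure risk, states: "Our study patients will be off neuroleptics and other psychotropic medications for at least 2 weeks (except benzodiazepines". Section 1.0 describes the 60 patients to be randomised as medication free.

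**The concern.** An antidepressant is a psychotropic and is not lorazepam, so the exception in Section 13.0 does not cover it. The same patient is therefore admitted by one section and excluded by another.

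The exclusion is offered as a safeguard against seizure, so this is more than a matter of wording. Section 15.0 itself treats medication as relevant: it attributes the 10 seizures reported since 1997 either to settings above the safe range or to interaction with drugs that lower the seizure threshold. If staff enrol from Table E.1, the risk sections describe a different population from the one treated. If staff apply Section 13.0, they turn away patients whom Section 5.0 means to recruit.

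**Working it through.** The documents give no figure to reproduce. The check sets the rules side by side and then tests the ways in which they might be reconciled.

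**The rules, applied to a depressed patient on a stable antidepressant who is otherwise eligible**

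| Place | Rule or statement | Result |
|---|---|---|
| 5.0, Table E.1 item 4 | stable antidepressant for 3 weeks before and during rTMS | admitted |
| 5.0, rationale text | trial is run in patients on stable psychotropics | admitted |
| 13.0, Research Procedures | all psychotropics excluded except lorazepam up to 3 mg/d | excluded |
| 15.0, seizure paragraph | off psychotropics at least 2 weeks, benzodiazepines excepted | does not fit |
| 1.0 | cohort is medication free | does not fit |

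**Reading 1: item 4 is conditional (if on an antidepressant, it must be stable).** This still admits the patient whom Section 13.0 excludes.

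**Reading 2: Section 13.0 simply adds an exclusion to the table.** Enrolment could then run on both rules, but only by taking no one on an antidepressant. Item 4's antidepressant clause would have no use, and the Section 5.0 statements about concurrent medication and washout would be untrue.

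**Reading 3: the table carries the exclusion elsewhere.** It does not. Of its 13 items, only item 4 sets a rule on current medication. Item 10 covers contraindications to rTMS, beginning "No contraindication to rTMS (history of neurological disorder or seizure (except induced by ECT), increased intracranial pressure, brain surgery"; the rest of its list names no drug either.

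**Reading 4: Sections 13.0 and 15.0 refer to the healthy controls.** Both speak of patients, and the Section 13.0 paragraph mentions the referring psychiatrist. The controls have their own criterion in Section 5.0 that they take no antidepressant.

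**Reading 5: the time windows separate the rules.** Item 4 extends through treatment and Section 13.0 has no window, so timing cannot reconcile those two. Timing bears only on Section 15.0, which does not say from when its 2 weeks are counted. Suppose the 14 drug-free days end X days before the first session. Their overlap with item 4's 21 days is min(14, max(0, 21 − X)):

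- X = 0: min(14, 21) = 14 of 14 days
- X = 7: min(14, 14) = 14 of 14 days
- X = 14: min(14, 7) = 7 of 14 days
- X = 21 or more: 0 days

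If the 2 weeks run up to the first session (X = 0, an assumption), the overlap is complete. Only with X of at least 21 do the windows separate. The patient would then be taking the drug during treatment, and Section 13.0 would still exclude that patient.

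**Benzodiazepines.** The 3 mg figure is the same in Table E.1, the Section 5.0 text and Section 13.0, but the scope is not. Table E.1 accepts an equivalent of lorazepam, Section 13.0 excepts lorazepam only, and Section 15.0 excepts benzodiazepines with no limit. A patient on an equivalent dose of another benzodiazepine is thus admitted by the table and excluded by Section 13.0.

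**The case against.** The fair case against giving this weight has four parts.

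- Section 5.0 ties enrolment to the listed criteria, so staff have a working table, and the medication-free phrase in Section 1.0 is only descriptive. This limits the practical confusion at enrolment. It does not make the safety statements in Sections 13.0 and 15.0 true of the patients enrolled.
- Table E.1 is silent on stimulants and neuroleptics; silence is an omission and does not contradict Section 13.0. That is right for the table. The contradiction proper concerns antidepressants and non-lorazepam benzodiazepines, together with any other drug covered by the broader term psychotropic in the Section 5.0 rationale.
- The window arithmetic depends on a start point that Section 15.0 does not give. That is also right. The conclusion does not need it, because item 4 covers the treatment period and Section 13.0 has no time limit.
- No number of affected patients is known, no harm is shown and the main analysis is untouched. All of this stands. The issue is which patients may be enrolled and whether a stated safeguard applies to them.

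Reconciling text could exist in pages that were not available, such as the consent form. Nothing in the visible text does it.

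**Conclusion.** The concern holds and should be corrected. The entry criteria and the seizure safeguard are contradictory in current text, for any depressed patient taking an antidepressant and for some patients taking a benzodiazepine other than lorazepam. One of Table E.1's 13 items addresses current medication, and it admits what Section 13.0 excludes.

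The number of the 60 patients affected cannot be derived from the documents. The conclusion rests on the wording alone and needs no assumption beyond an antidepressant being a psychotropic drug.

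Several things are not affected: the intention-to-treat main analysis, the randomised comparison, and the other seizure precautions (MRI prescreening, tailoring to motor threshold, exclusion of patients with a seizure history).

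**What to change.** The sponsor and IRB should decide on one rule for concurrent medication, including its time window and its benzodiazepine scope. This review does not say which rule is right. Then:

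- make Section 1.0, Table E.1 item 4, the Section 5.0 rationale and the seizure statements in Sections 13.0 and 15.0 agree with it;
- check that the consent text describes the same population and the same safeguard;
- in Section 12.0 (data analytic plan, item 2), define the prohibited-drug violation by the same rule. It helps to define the fully adherent sample, which is secondary only.

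A separate, minor point for the same amendment is the look-back for a suicide attempt, which is 12 months in Table E.1 item 12 and 6 months in the Section 5.0 text. These should also be reconciled.

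The cost is a wording amendment and a consent check. The choice of rule may affect recruitment, since Section 5.0 counts on avoiding a general washout to help it.

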15.0 Risks to Subjects

Potential risks related to TMS: Based on previous clinical work of left prefrontal rTMS in depression, and in various other psychiatric disorders as well as others researchers published and communicated experiences, we hypothesize that NON-SYNC left prefrontal rTMS (as intended in this grant) is an effective antidepressant treatment, and that SYNC rTMS will be at least as effective or better. This study is an important necessary step to characterize the safety, and efficacy of the antidepressant effect. **Potential worsening of depression symptoms with TMS**: Several studies have so far demonstrated the feasibility of rTMS in depression without any alarming indicators of exacerbation of symptoms. We

will work closely with the patient to familiarize them with the experimental setup. The BSL team members at MUSC are experienced with the procedure and are among the leading experts in the field of brain stimulation and TMS. We will also monitor closely for worsening suicidal ideation or increasing hypomania or mania.

Potential risk of a seizure: Unlike ECT, in routine use, TMS stimulates the neurons at a sub-convulsive level, although less than 50 seizures have been noted in the literature. Six of them have been in healthy volunteers (without any history of seizures, brain masses or traumatic brain injuries). The risk of seizure induction is related to the intensity, duration, frequency and rest interval of stimulation. Following the adoption and widespread use of the safety guidelines from an NINDS workshop on TMS, 10 seizures have been reported since 1997 and they involved parameters of "higher settings" then the "safe range" ¹⁹⁻²¹, or interactions of TMS with medications known to lower the seizure threshold. To our knowledge, stimulation with the parameters and settings we propose to use does not cause seizures, even the SYNC settings. We will carefully titrate each person's stimulus intensity to his or her motor threshold, before beginning treatment. Our study patients will be off neuroleptics and other psychotropic medications for at least 2 weeks (except benzodiazepines).

Safety in case of pregnancy: This protocol will exclude pregnant women (women of child bearing age will perform a pregnancy test prior to enrollment)

Potential risks related to MRI scanning. There are very few potential risks from MRI itself. There is no exposure to ionizing radiation and the machine and scanning sequences and gradients are approved by the FDA for routine clinical use.

Metallic objects: If a patient has any metal implants (not including dental fillings), a pacemaker, or other irremovable medical devices, the patient would be at risk from the device or implant shifting during the scanning procedure but the patient will be asked to inform the study investigators about these at the beginning of the study and again prior to scanning so that they won't be scanned. If a patient has a removable metal object on his body then it may propelled by the MRI magnet, causing injury. To minimize this risk, patients will be asked and inspected for any evidence of metal objects that might cause harm in the scanner and such objects will be removed prior to scanning.

Claustrophobia due to MRI scanning: If a patient is claustrophobic, the MRI scanning procedure might cause anxiety. We will work with the patient to minimize the effect of anxiety. Patients

will be given the option of prism glasses that allows them to look outside. We have found that a regular communication with the patients while in the scanner and updating them of the progress of the experiment (calibration, shimming and tuning, getting the structural scans), is also extremely helpful in minimizing the anxiety level. The PI's and their neuroimaging colleagues have extensive experience in imaging patients with mood disorders during structural and even longer lasting functional paradigms³⁹.

Hearing loss: A patient may experience some loud noises during the MRI scanning procedure and there is a mild risk of hearing damage if patients are not given protective earwear. Patients will be using sound-dampening headphones and wearing earplugs to decrease the intensity of these noises and minimize this risk.

16.0 Potential Benefits to Subjects or Others

Summary of Risk Analysis.

The potential benefits of this study outweigh the risks for both patients and controls.

For the individual depressed subject. Depressed patients who have failed to respond to medication are at risk of suicide and prolonged disability. Daily left prfrontal rTMS for 4-6 weeks has antidepressant effects. One arm of the study involves conventional TMS and many patients will get relief from their depression. The experimental arm (SYNC) will likely also result in depression remission, but perhaps at a lower rate. Or perhaps higher. But all patients enrolled have a significant chance of getting their depression treated. For society. The risks of the rTMS listed above are slight relative to electroconvulsive therapy, a treatment often used in this population. If this trial is successful and SYNC rTMS proved to be a more effective alternative to NON-SYNC TMS, depressed patients not responding to medication would have a better treatment alternative that might begin to compare with ECT in terms of acute remission rates, with fewer side effects and risks. The protocol is safe, and the potential benefit to society of improving a safe tool as a potential treatment modality for depression is enormous and well worth the potential risk involved in this protocol.

17.0 Sharing of Results with Subjects

At the formal completion of the entire clinical trial after all data have been reviewed and the dataset locked, we will be able to let subjects know whether they received the SYNC or NON-SYNC TMS. This may be helpful if they require additional TMS in the future.

